5.6.1 Treatment Regimen/Dosage Adjustments

Patients who have received nonstudy topical IOP-lowering medication (prohibited before Week 52 unless required for safety reasons due to inadequate IOP control and attested to by the investigator) in a Bimatoprost SR study eye will receive Sham administration in that eye on the Bimatoprost SR repeat administration day(s). Patients who have received nonstudy topical IOP-lowering medication in a fellow eye or a Control Group study eye will continue to receive Sham administration in that eye on the administration day(s).

[figure not shown]
Patients who have received nonstudy IOP-lowering medication in both eyes will not undergo Bimatoprost SR administration or Sham administration in either eye.

Patients who use nonstudy IOP-lowering medication (prohibited before Week 52 unless required for safety reasons due to inadequate IOP control and attested to by the investigator) in only one eye will be followed for the duration of the study. If used in both eyes, patients will be followed at minimum for 12 months after the last administration of Bimatoprost SR or Sham. Patients using nonstudy IOP-lowering medications in both eyes prior to the Week 16 or Week 32 Administration Day will not attend the administration visit(s), nor will they attend the Day 2, Days 4 and 8 (phone call), or 2-week visits (ie, Weeks 2, 18, and 34) following an administration. They would continue the schedule at Week 22 or Week 38, as appropriate for the administration cycle.

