assumption on the common IOP standard deviation of 3.8 mm Hg, a sample size of 486 patients (162 per group) would provide approximately 95.1% and 83.5% power to show NI of Bimatoprost SR 15 µg and Bimatoprost SR 10 µg, respectively, to timolol at all 6 scheduled timepoints based on an NI margin of 1.5 mm Hg; and at 3 or more timepoints based on an NI margin of 1.0 mm Hg. With the updated premature discontinuation or rescue rate of 5% within 12 weeks, approximately 510 patients (170 per group) are to be enrolled into this study.

8. Study Visit Schedule and Procedures

Patients who complete the entire study without receiving nonstudy IOP-lowering medication will have a minimum of 25 visits and 6 phone calls. The schedule begins with Screening, followed by a Washout period of up to 42 days for both eyes, and then Baseline. These visits are followed by 3 cycles of Bimatoprost SR or Sham administration. Each administration cycle includes Bimatoprost SR or Sham administration (Day 1), visit on Day 2, phone calls on Days 4 and 8, and visits on Weeks 2, 6, 12, and 15 (which is the visit prior to the next administration day). Additional treatment period visits occur through Week 52 and extended follow-up continues into Months 14, 16, 18, and 20/exit.

The study visits should adhere as closely as possible to the schedule shown in [Table 2](#) through [Table 6](#). See [Figure 1](#) for a flowchart of patient participation.

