Prior and concomitant medications will be separately summarized using the safety population for each treatment group as the number and percentage of patients under each indication preferred term (MedDRA) and unique base preferred name from the World Health Organization Drug Dictionary Enhanced (WHODDE).

Concurrent procedures will be provided in the listings.

Non-study IOP Lowering Medications/Procedures

A non-study IOP-lowering medication is defined as a medication for which the investigator specifically marked “Yes” to the question “Is this medication used as a non-study IOP-lowering medication?” on the concomitant medication electronic case report from (eCRF). A non-study IOP-lowering procedure is defined as a procedure for which the investigator specifically marked “Yes” to the question “Was this an IOP-lowering procedure?” on the concurrent procedure eCRF.

Other medications or procedures that could potentially reduce IOP but are not marked in the eCRF as non-study IOP-lowering medications/procedures will be listed in the separate document used to identify data excluded from the PP analysis.

Washout Ocular Medication

Similarly, washout ocular medications will be tabulated by treatment group for the study eye and pooled for the fellow eye.

9.0 **EXTENT OF EXPOSURE AND TREATMENT COMPLIANCE**

9.1 **EXTENT OF EXPOSURE**

Throughout the study, each patient will receive up to 3 administrations of Bimatoprost SR or Sham injection in each eye with a fixed interval of 16 weeks. The number and percent of patients receiving Bimatoprost SR or Sham treatment in the study eye during the study will be tabulated by the number of treatment administrations for each treatment group.

Each patient's study duration will be calculated as the number of days between the exit date and Day 1 Administration Day, inclusively (date of the exit - Day 1 Administration date + 1). Patients' study duration will be summarized using descriptive statistics for each treatment group.

10.0 **EFFICACY ANALYSES**

The primary efficacy variable for country/regions other than US will be time-matched IOP change from baseline in the study eye. The primary efficacy variable for the United States (US) Food and Drug Administration (FDA) (Division of Transplant and Ophthalmology Products) is IOP in the study eye (Section 10.3.1).

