10.4 ADDITIONAL EFFICACY PARAMETERS

11.0 SAFETY ANALYSES

The safety analysis will be performed using the safety population. The safety parameters will include the following nonocular safety parameters: nonocular AEs, clinical laboratory values, vital signs, and pregnancy; and ocular safety parameters: ocular AEs, implant/sham assessment, visual acuity, visual field examination, macroscopic iris color assessment, macroscopic conjunctival hyperemia assessment, Bimatoprost SR implant assessment, biomicroscopic examination, lens assessment, optic disc examination, dilated ophthalmoscopic examination, gonioscopy assessment, optical coherence tomography (OCT), specular microscopy, pachymetry, anterior segment optical coherence tomography (AS-OCT). Unless otherwise stated, the last nonmissing safety assessment before the first dose of study treatment will be used as the baseline for all analyses of that safety parameter. Continuous variables will be summarized by number of patients and mean, SD, median, the 1st quartile and the 3rd quartile, minimum, and maximum values. Categorical variables will be summarized by number and percentage of patients.

For ocular safety assessments, analyses will be performed by treatment group for study eye and pooled for fellow eye based on the first actual treatment received in each eye. For nonocular safety measures, analyses will be performed on a patient basis for the treatment actually received.

For all safety by-cycle summary analyses, in order to compare cycles of similar duration, the data included in each cycle will be,

- Cycle 1 (16 weeks): data from the 1st injection to the 2nd injection date -1 or upper bound of week 15 visit window (section 16.1) if a patient didn't receive the 2nd injection;
- Cycle 2 (16 weeks): data from the 2nd injection to the 3rd injection date -1 or upper bound of week 31 visit window (section 16.1) if a patient didn't receive the 3rd injection;
- Cycle 3 (20 weeks): data from the 3rd injection to upper bound of week 52 visit window (section 16.1);
- Extended safety follow up: data after week 52 for patients with 3 injections and extended follow up.

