11.1 ADVERSE EVENTS

Adverse events will be coded by SOC and preferred term using the Medical Dictionary for Regulatory Activities.

For a given AE and patient, if more than 1 severity grade is reported, the worst severity grade (the greater of the onset and maximum severity recorded on the electronic case report from [eCRF]), will be used for analysis.

Adverse events will be classified into ocular AEs and nonocular AEs. An ocular AE will be determined as indicated on the AE form of eCRF, and thus are not limited to AEs with primary SOCs of eyes. The treatment-related ocular AEs will be further broken down by either related to injection procedure or related to study drug as indicated on eCRF. Ocular AEs will be tabulated by treatment group for the study eye and pooled for the fellow eye, and nonocular AEs will be summarized by treatment group for patient. Analysis by cycle of treatment will also be performed.

Treatment-Emergent Adverse Events

An AE will be considered a treatment-emergent adverse event (TEAE) for the study treatment period if the AE meets 1 of the following criteria:

- The onset date is on or after the first study treatment date.
- The onset date is before the first study treatment date and either:
 - The severity of the event worsened on or after the first treatment date.
 - The event became serious on or after the first study treatment date.

An AE will be considered as a TEAE for a treatment cycle if the AE meets 1 of the following criteria:

- The onset date is on or after the treatment administration of the cycle but prior to the next cycle administration.
- The onset date is before the treatment administration of the cycle and either:
 - The severity of the event worsened on or after the treatment administration of the cycle.
 - The event became serious on or after the treatment administration of the cycle.

Overall summary of TEAEs will be provided on a per-patient basis for categories of all TEAEs, treatment-related TEAEs, injection procedure-related TEAEs, study drug-related TEAEs, serious TEAEs (STEAEs), deaths, and TEAEs leading to study discontinuation. Each category (except deaths) will be further classified into ocular and nonocular subcategories.

The number and percentage of patients reporting TEAEs will be provided on a per-patient basis by 1) SOC and preferred term; 2) SOC, preferred term and severity in descending order of frequency for each treatment group.

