The number and percentage of patients reporting nonocular TEAEs in each treatment group will be tabulated by SOC and preferred term. Also the number and percentage of patients reporting treatment-related (including study drug related or injection procedure related) nonocular TEAEs in each treatment group will be tabulated by SOC and preferred term.

Similar analyses will be done for ocular TEAEs including 1) by PT and severity; 2) treatment-related TEAEs by PT for each treatment group by study eye and fellow eye. In addition, similar analyses will be performed for ocular TEAEs by treatment cycle.

Within each treatment cycle, ocular TEAEs identified (onset or worsened) within 2 days of administration and identified more than 2 days of administration of each cycle will be summarized by each treatment group for study eye and pooled for fellow eye.

Serious TEAEs

Nonocular and ocular STEAEs will be summarized by preferred term and treatment group, respectively.

TEAEs Leading to Study Discontinuation

Nonocular TEAEs and ocular TEAEs leading to premature discontinuation of the study will be summarized by preferred term and treatment, respectively.

Similarly, ocular TEAEs leading to premature discontinuation will also be tabulated by treatment group by treatment cycle.

Ocular TEAEs Leading to Study Drug Discontinuation or Regimen Change

Ocular TEAEs leading to study drug discontinuation will be summarized by preferred term and treatment for the entire study period and also for each cycle. Ocular TEAEs leading to study drug discontinuation or regimen change are defined as the ocular TEAEs with action regarding study drug reported as “Discontinued” or “Regimen Changed” on the eCRF AE form.

Ocular TEAEs Leading to Implant Removal

Ocular TEAEs leading to implant removal will be summarized by preferred term and treatment for the entire study period and also for each cycle.

TEAEs of Special Interest

Corneal TEAEs and Anterior chamber inflammation TEAEs of interest will be summarized by preferred term and treatment group, respectively. Similar analyses will be done by treatment cycle. The full list of corneal AEs and Anterior chamber inflammation AEs of interest will be provided prior to each database lock.

Additional subcategory of TEAEs may be analyzed separately, such as for ocular TEAE associated with use of a prostaglandin analog (PGA), etc.

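### Bimatoprost SR study eyes switched to Sham after rescue still count as SR in Cycles 2 and 3, so implant exposure can be overstated and repeat-implant procedure-event rates read slightly low

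*SAP*

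**What the plan says.** **Treatment rule.** Protocol 5.6.1 covers an eye that has received nonstudy topical IOP-lowering medication "in a Bimatoprost SR study eye will receive Sham administration in that eye on the Bimatoprost SR repeat administration day(s". If both eyes have been rescued, neither receives an implant or a Sham. The affected eyes are therefore SR study eyes rescued while the fellow eye is not.

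**Grouping rule.** For ocular safety, SAP 11.0 states that "analyses will be performed by treatment group for study eye and pooled for fellow eye based on the first actual treatment received in each eye".

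**Cycle rule.** SAP 11.0 defines Cycle 2 as "data from the 2nd injection to the 3rd injection date -1 or upper bound of week 31 visit window", the upper bound applying when there is no third injection. SAP 11.1 assigns an event to a cycle when "The onset date is on or after the treatment administration of the cycle but prior to the next cycle administration". Worsening, or becoming serious, on or after that administration also qualifies.

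**Tables affected.** SAP 11.1 splits treatment-related ocular events into procedure-related and drug-related and plans analyses by cycle. It also plans a table by time since dosing: "Within each treatment cycle, ocular TEAEs identified (onset or worsened) within 2 days of administration", set against those found later.

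**Exposure.** SAP 9.1 says that "each patient will receive up to 3 administrations of Bimatoprost SR or Sham injection in each eye with a fixed interval of 16 weeks". It plans one exposure table, in which "patients receiving Bimatoprost SR or Sham treatment in the study eye during the study will be tabulated by the number of treatment administrations", separately by arm.

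**Post-rescue events.** Protocol 7.3.4 promises a separate summary of safety events that occur after nonstudy IOP-lowering medication has been started. SAP Section 11 does not mention one, and SAP 17.0 lists only two added efficacy-model terms as changes from the protocol.

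**The concern.** Safety after repeated administration is a stated objective. According to Protocol 1.3.3, most adverse events in the Phase 1/2 study were ocular, arose within 2 days of administration and were attributed to the procedure. The Cycle 2 and 3 procedure-related and within-2-day tables are therefore where a reader will look for the risk of a second or third implant.

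An SR-group eye that receives Sham in a cycle has no needle entry and no new implant in that cycle, yet it sits in the SR denominator. If such eyes have fewer of these events, the rate shown is below the rate in eyes that were re-implanted. The exposure table has a related problem: an eye with one implant and two Shams can appear as having had three administrations, which overstates experience with repeat implants.

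**Working it through.** **1. Does a Sham open a cycle?** The point depends on this. Protocol Section 8 says: "Each administration cycle includes Bimatoprost SR or Sham administration (Day 1), visit on Day 2". SAP 9.1 speaks of a Sham injection. If injection meant implant only, the Control group would have no Cycle 2 or 3. It would also have no study completers, because SAP 7.0 requires at least one injection. A Sham therefore opens a cycle, and the switched eye stays in the Cycle 2 or 3 tables of its SR group.

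**2. What does SAP 9.1 count?** Literally, it counts implants and Shams together: 1 implant + 2 Shams = 3 administrations. Counting implants for SR and Shams for Control is a possible reading, but the text does not say so.

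**3. How many eyes?** The documents give no number of switched eyes and no TEAE rate, so there is no plan figure on this point to reproduce. The only anchor is SAP 14.0: about 5% of patients discontinued or rescued in the first 12 weeks, masked and pooled over arms. The same 5% gives the plan's enrolment: 162 / 0.95 = 170.5, against about 170 per group.

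- Equal rates across arms, every case a study-eye-only rescue: 0.05 × 170 = 8.5 eyes per SR arm, or 0.05 × 340 = 17 eyes in both.
- Every such case in the SR arms and none in Control: 0.05 × 510 = 25.5, and 25.5 / 340 = 7.5%.

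The 5% also includes dropouts, fellow-eye-only rescue and both-eye rescue, so the real share by Week 12 is probably below it. Rescue between Weeks 12 and 16 adds to Cycle 2. Rescue up to Week 32 adds to Cycle 3, and no rate is given for it. Actual denominators will also be below 340.

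**4. How far does the rate move?** Let f be the share of switched eyes in the cycle denominator, p the event rate in re-implanted eyes and s the rate in switched eyes.

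- Rate shown = (1 − f) × p + f × s
- Relative shortfall = f × (1 − s/p), which never exceeds f

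With p = 20% and s = 0% or 5% (all assumed):

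| f (assumed) | Eyes of 340 | Shown, s = 0% | Shown, s = 5% |
|---|---|---|---|
| 1% | 3.4 | 19.8% | 19.85% |
| 2.5% | 8.5 | 19.5% | 19.625% |
| 5% | 17 | 19.0% | 19.25% |
| 10% | 34 | 18.0% | 18.5% |

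The 10% row only illustrates a larger Cycle 3 share. At higher event rates the absolute gap grows. With f = 5%, p = 30% and s = 5%, the table shows 0.95 × 30 + 0.05 × 5 = 28.75%. With f = 5%, p = 50% and s = 0%, it shows 0.95 × 50 = 47.5%.

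**The case against.** **The grouping is a stated convention.** SAP Amendment 1 updated the sentence on grouping by first actual treatment. Sham after rescue is part of the protocol's own SR regimen, so a Cycle 2 table by SR group correctly describes that group under that regimen. This stands. The rate is low only if it is read per re-implanted eye, and the SAP does not label it that way. The planned tables should stay.

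**The effect is small.** Before Week 52, rescue is allowed only for safety, should be confirmed at a subsequent visit, and is attested eye by eye (Protocol 4.5.2). This also stands for Cycle 2. For Cycle 3 the documents neither support nor rule out a larger share.

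**Part of it is already visible.** SAP 11.3.1 tabulates implant delivery by cycle, and SAP 11.3.7 reports implant size by cycle and visit. A reader could infer how many implants were placed, but the TEAE denominators do not change. Table specifications are in a separate document and the content of Table 16-1 is not shown, so a flag for switched eyes could exist there.

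**Stronger readings that a reader might infer.**

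- *All Cycle 2 and 3 ocular tables should be reclassified by treatment given.* The documents do not support this. Rescue happens after randomisation, and Protocol 5.10 withholds re-implantation for earlier adverse events or safety concerns, so groups formed by implants received are selected.
- *Corneal and endothelial findings are diluted too.* This is uncertain. A switched eye still carries its earlier implant, and Protocol 1.3 expects more than 75% matrix degradation only within about 12 months.
- *The post-rescue summary has been dropped.* Silence in SAP 17.0 fits equally well with the summary still being planned. It is a gap in the SAP text, and filling it would not alter any by-cycle denominator.

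**Conclusion.** The point holds at modest size. As written, SAP 9.1 can overstate how many SR eyes received 2 or 3 implants. The Cycle 2 and 3 procedure-related and within-2-day ocular TEAE rates understate the rate per re-implanted eye, provided that switched eyes have fewer such events. The relative understatement is bounded by the share of switched eyes. Putting that share under 5% in Cycle 2 is a judgement from a pooled Week 12 figure. The shares and event rates used above are assumptions.

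The textual chain is firm; the size is not known. Nothing here reaches the Week 12 efficacy analyses or the power calculation, because no repeat administration occurs before Week 16. Cycle 1 and whole-study TEAE tables are unaffected as well.

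**What to change.** - **SAP 9.1:** for the SR groups, tabulate the number of implants actually received (1, 2, 3). Count Shams given to SR study eyes separately.
- **SAP 11.0 and 11.1:** keep the by-group tables by first actual treatment. For the Cycle 2 and 3 procedure-related and within-2-day ocular TEAE tables only, add a descriptive rate among eyes that received an implant in that cycle, with the number of Sham-switched eyes in a footnote. Leave corneal, endothelial and other ocular TEAE tables unchanged.
- **SAP Section 11, as a separate consistency point:** add the post-rescue safety summary promised in Protocol 7.3.4, or record its removal in SAP 17.0.

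The cost is low: one derived variable (implant or Sham at each administration) from administration records, a few SAP sentences, one added rate with a footnote, and a summary that the protocol already promises. No new data are needed. The change applies to the Week 52 and final locks. The downside is that the added rate rests on a subset defined after randomisation, so it should be labelled descriptive and not used for formal comparison with Control.

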8.4.3.8 Cycle 2: Week 16 Administration Day

The following procedures are performed at Week 16 (-2 to +4 days):

- Collection of adverse events
- Collection of concomitant medications and procedures
- Vital signs

- Administer assigned study treatment

[figure not shown]

Approval Date: 05-Jun-2018

8.4.3.9 Cycle 2: Day 2

On Day 2 after the second study treatment administration, the following procedures are performed:

- Collection of adverse events
- Collection of concomitant medications and procedures
- Vital signs

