8.4.3.15 Cycle 3: Week 32 Administration Day

The following procedures are performed at Week 32 (-2 to + 4 days):

- Collection of adverse events
- Collection of concomitant medications and procedures
- Vital signs

- Administer assigned study treatment

Approval Date: 05-Jun-2018

8.4.3.16 Cycle 3: Day 2

On Day 2 after the third study treatment administration, the following procedures are performed:

- Collection of adverse events
- Collection of concomitant medications and procedures
- Vital signs

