11.3.5 Biomicroscopy and Ophthalmoscopy

Biomicroscopy will be performed in each eye by slit-lamp examination at each scheduled visit. Dilated ophthalmoscopy (including vitreous, optic nerve, macula, and retina periphery) and lens status assessment will be performed for each eye at Screening, Baseline, Week 12, Week 28, Week 44, Week 52, and Month 20/Exit.

All biomicroscopy and ophthalmoscopy examinations findings will be coded using MedDRA dictionary.

The number and percentage of patient eyes with biomicroscopy and ophthalmoscopy findings more than 1 severity grade increase (worsening, i.e., a change from 0 to 2 and above, or from 0.5 to 2 and above, or from 1 to 3 and above) from baseline for findings with a severity grade, or a status change from absence at baseline to presence at follow-up visit for findings under other pathology which is not associated with a severity grade, at 1 or more postbaseline visits, will be tabulated by preferred term in descending order of incidence rate. The number and percentage of eyes with any clinically significant findings will be presented (as "Overall") by treatment group for study eye and pooled for fellow eye. Similar analyses will be performed for each treatment cycle and may be provided for findings with other severity grade increase.

At follow-up visits, the lens opacity will be assessed only for eyes evaluated as phakic at baseline. The presence and severity of nuclear, cortical, and posterior subcapsular cataract lens opacities using a 3-point scale (absent, < standard photo #2, and \geq standard photo #2) will be summarized by treatment group for study eye and pooled for fellow eye by visit. The lens status will be presented as data listings and may be summarized with frequency and percent as necessary.

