11.3.7 Gonioscopy and Bimatoprost SR Implant Assessment

Gonioscopy will be performed to assess the iridocorneal (anterior chamber) angle for both eyes at visits as specified in the protocol. Patients presenting peripheral anterior synechiae on gonioscopy will be presented in listing.

The Bimatoprost SR implant assessment will be performed during gonioscopy examination. For patients who have implant size collected, implant size (percentage of the original material) will also be summarized based on the percentage category for each implant in the study eye by cycle and visit for bimatoprost treatment groups. The number and percentage of implants at each of 12 zones of implant location will be summarized by visit. Also, the number of patients who have implant(s) contact with corneal endothelium at any visit within a cycle will be summarized by cycle. Implant assessment will be presented as data listings for the location of implant (12 zones), status of contact with other implant(s), and status of contact with corneal endothelium.

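### By-cycle safety tables meant to compare cycles of similar length set a nominal 20-week Cycle 3 beside two 16-week cycles, so at equal weekly risk crude Cycle 3 percentages are expected to be somewhat higher

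*SAP*

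**What the plan says.** SAP 11.0 introduces the by-cycle safety windows with a purpose: "in order to compare cycles of similar duration, the data included in each cycle will be". The definitions that follow are:

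- "Cycle 1 (16 weeks): data from the 1st injection to the 2nd injection date -1"
- "Cycle 2 (16 weeks): data from the 2nd injection to the 3rd injection date -1"
- "Cycle 3 (20 weeks): data from the 3rd injection to upper bound of week 52 visit window"

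A patient who misses the next injection is cut off at the end of the Week 15 or Week 31 window. Extended follow-up is kept out of Cycle 3.

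The results reported by cycle are counts and percentages. They include ocular TEAEs, with a split at 2 days after administration (SAP 11.1), worst visual acuity line change (11.3.2), visual field abnormalities (11.3.3), hyperemia worsening at any follow-up visit (11.3.4), and biomicroscopy and ophthalmoscopy findings present at one or more visits (11.3.5). They also include implant "contact with corneal endothelium at any visit within a cycle will be summarized by cycle" (11.3.7). On the examination schedule, 11.3.5 says that dilated ophthalmoscopy and "lens status assessment will be performed for each eye at Screening, Baseline, Week 12, Week 28, Week 44, Week 52, and Month 20/Exit". The text gives no exposure-adjusted rate and no common cut for the by-cycle tables.

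**The concern.** The stated aim and the definitions do not match: Cycle 3 is nominally a quarter longer than the other two. Crude incidence, worst-value and any-visit measures all tend to rise with time at risk and with the number of examinations. A gap between Cycle 3 and the earlier cycles can therefore appear with no change in weekly risk. A true fall in Cycle 3 risk can also be hidden.

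This matters because the study objective covers safety after initial and repeated administrations, and the by-cycle tables are the natural place to look for a trend with repeat dosing. It matters most for implant tables such as endothelial contact and TEAEs leading to implant removal. Controls receive Sham, so for these the comparison across cycles has no control counterpart to lean on.

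**Working it through.** **Reproducing the plan's figures.** Scheduled injections are at Day 1, Week 16 and Week 32. Lengths are 16 − 0 = 16, 32 − 16 = 16 and 52 − 32 = 20 weeks, as the SAP states. The ratio is 20/16 = 1.25.

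**Counting visits and examinations** (Protocol Summary, Visit Schedule; SAP 11.3.5):

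| | Cycle 1 | Cycle 2 | Cycle 3 |
|---|---|---|---|
| Visits after Day 2 | Weeks 2, 6, 12, 15 (4) | Weeks 18, 22, 28, 31 (4) | Weeks 34, 38, 44, 48, 52 (5) |
| Dilated examinations | Week 12 (1) | Week 28 (1) | Weeks 44, 52 (2) |

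**Effect of visit windows.** The content of SAP Table 16-1 is not shown in the public copy, so I use the protocol windows: −2 to +4 days for the repeat injections (8.4.3.8, 8.4.3.15) and ±7 days for Week 52 (8.4.3.22).

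- Cycle 1 is 112 − 2 = 110 to 112 + 4 = 116 days.
- Cycle 3 to Week 52 + 7 days (day 371) is 371 − 222 = 149 days (21.3 weeks) for a third injection 2 days early, and 371 − 228 = 143 days (20.4 weeks) for one 4 days late.
- If both repeat injections are 4 days late and the delays add, it is 371 − 232 = 139 days (19.9 weeks).

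So 20 weeks is a nominal length, not a guaranteed minimum.

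**Constant weekly hazard, no true change.** p20 = 1 − (1 − p16)^(20/16). For p16 = 5%, 10% and 20% this gives 6.2%, 12.3% and 24.3%. For 10% over 21 weeks it gives 12.9%.

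**Hazard concentrated early.** Protocol 1.3.3 says most events in the Phase 1/2 study came within 2 days of administration but gives no share, so the share s is an assumption. Put s of the 16-week hazard in the first 2 days and stretch the rest from 110 to 138 days:

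H16 = −ln(1 − p16); H20 = H16 × [s + (1 − s) × 138/110]; p20 = 1 − exp(−H20).

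For p16 = 10%, H16 = 0.1054. With s = 0.7 the bracket is 0.7 + 0.3 × 1.2545 = 1.076, so H20 = 0.1134 and p20 = 10.7%. For s = 0.5, 0.8 and 0.9 the results are 11.2%, 10.5% and 10.2%.

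**Two dilated examinations instead of one.** With a 3% rate per examination (assumed), two independent looks give 1 − 0.97² = 5.9%. If findings fully persist, the second look adds nothing and the figure stays at 3%. Looks at the same eye are correlated, so the truth lies between.

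**Masking in the other direction.** A Cycle 3 weekly hazard 16/20 = 0.8 times that of the earlier cycles would be exactly offset by the longer window.

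**With Cycle 3 cut at nominal Week 48.** Lengths become 16/16/16 weeks, visits after Day 2 become 4/4/4, and dilated examinations become 1/1/1. At equal weekly risk the expected percentages are then equal, for example 10/10/10 instead of 10/10/12.3. Rates per patient-time over the full 20 weeks would correct for time but not for the extra dilated examination.

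**The case against.** The strongest reply is that the trial has concurrent controls. Control study eyes and Sham-treated fellow eyes are observed over the same windows, so longer observation raises their Cycle 3 percentages too. A reader might infer that the between-arm safety comparison in Cycle 3 is distorted, or that a higher Cycle 3 rate can never be separated from longer observation. The documents support neither. Within Cycle 3 the arms share one window, and for most tables the excess over Control remains readable. The implant tables are the exception.

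A reader might also infer that the third administration is bound to look worse. That is too strong. A Bimatoprost SR study eye given nonstudy IOP-lowering medication receives Sham at later administrations (Protocol 5.6.1), yet ocular safety is grouped by the treatment the eye first actually received (SAP 11.0). Readministration may also be withheld on safety grounds (Protocol 5.10). Both can lower Cycle 3 rates, and the by-cycle denominator is not stated.

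Three further points stand in part:

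- The split of TEAEs at 2 days protects the early stratum, but it concentrates the length effect in the later one.
- Endothelial cell density, corneal thickness and lens opacity are summarised by visit and are unaffected.
- The SAP prints the 20 weeks openly, speaks of similar rather than equal length, and plans no by-cycle hypothesis test in the text shown. Disclosure is not adjustment, though, and a 25% difference is avoidable when a visit already exists at 16 weeks.

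**Conclusion.** The point holds for comparisons across cycles. At equal underlying weekly risk, crude Cycle 3 percentages are expected to be somewhat higher. A 16-week 10% reads 12.3% at constant hazard and about 10.7% if 70% of the hazard is early. A dilated-examination finding at 3% per look reads between 3% and 5.9%. The effect is small in tables dominated by events around the injection. It is larger for TEAEs more than 2 days after administration, any-visit or worst-value measures, and ophthalmoscopy findings, and it bears most on implant tables with no control counterpart. For implant contact the argument rests on the longer window alone, because the gonioscopy schedule is not shown.

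These sizes assume a patient who reaches Week 52, the nominal schedule, and the stated hazard shapes. The net direction in any one table is not certain. The primary efficacy analysis is not involved. This is worth correcting because it is cheap and makes the tables serve their own stated purpose.

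**What to change.** In SAP 11.0, for by-cycle comparison tables, end Cycle 3 at the upper limit of the Week 48 window. First check in Table 16-1 that this falls about 16 weeks after the third injection. If it does not, use 16 weeks from the actual third injection date plus the protocol visit window. Show data from that limit to Week 52 as a separate labelled interval, and keep the full 20-week Cycle 3 column as supportive.

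Two consequential edits are needed:

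- In SAP 11.1, have the per-cycle TEAE rule refer to this limit. At present it closes a cycle at the next administration, which Cycle 3 does not have.
- In SAP 11.3.3, report visual field by visit instead of by cycle. Within the treatment period it is examined only at Weeks 28 and 52, so the cut would empty its Cycle 3 cell.

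The cost is one extra column or interval in the by-cycle tables and small edits to 11.1 and 11.3.3. Treatment, visits and data collection do not change, and Week 52 data stay in the by-visit and whole-study tables. Equal windows will not remove carry-over from a baseline taken before the first dose, or from implants that overlap between cycles. A footnote should say so.
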